#### A2a. Primary Aim and Hypotheses

**Aim 1: Test the LA&E model to investigate theory driven moderators of response to CT, MM, and AS.**

To accomplish Aim 1, we will use omnibus groups regions of significance (OGRS) tests to evaluate the effect sizes associated with the extent to which baseline pain catastrophizing, mindfulness, and activity level are respectively associated with reductions in opioid use following CT, MM, and AS.

**Hypothesis 1a:** Higher baseline levels of catastrophizing will be associated with greater reductions in opioid use in response to the CT intervention compared to MM or AS.

**Hypothesis 1b:** Lower baseline levels of activity will be associated with greater reductions in opioid use in response to AS compared to CT or MM.

**Hypothesis 1c:** Higher baseline levels of non-judgment will be associated with greater reductions in opioid use in response to MM compared to CT or AS.

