*For Aim 1 of this supplemental study*, the primary moderator measures are: (1) the Coping Strategy Questionnaire, Pain Catastrophizing items; (2) the Pain-Related Cognitive Process Questionnaire, Non-Judging scale; and (3) ActiGraph assessed activity counts. Other moderators will also be examined in secondary analyses. The primary outcome will be baseline to post-treatment change in opioid use, as assessed in MMEs. The Aim 1 supplemental hypotheses will be tested via a series of three OGRS tests. Indicator coding will be used and these tests will be interpreted in the context of point estimates and confidence intervals. Effect sizes will be calculated for any moderation main effects or interactions emerging that have confidence intervals that do not contain zero, and these effects will also be probed using the Johnson-Neyman boundary of significance to determine at what level of the moderator is outcome influenced. The Johnson-Neyman procedure eliminates the need to probe at a variety of arbitrary points along the moderator and defines regions of significance and regions of non-significance. In our pilot work we have successfully implemented this statistical approach in a sample of N=69 individuals with low back pain to detect moderator main and interaction effects to provide a preliminary test of the LA&E model in a trial comparing MM, CT and Mindfulness-Based Cognitive Therapy (MBCT). This sample size provided sufficient power ( $\alpha \leq .05$ ) to identify: (1) an interaction effect for MM vs. MBCT ( $b = .09$ ,  $p < .05$ , Confidence Interval [CI]: .003 to .175), such that people with low baseline catastrophizing showed greater improvement

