in pain intensity when assigned to MBCT ( $r = -.36$ ; within condition effect), with the boundary of significance identified as a Pain Catastrophizing Scale score of  $\leq 16.35$ ; (2) a further interaction effect for MM vs. MBCT ( $b = -.23$ ,  $p = .05$ , CI:  $-.46$  to  $.003$ ), showing that higher baseline mindfulness was associated with greater improvement in pain intensity in MBCT ( $r = .40$ ; within condition effect), with the boundary of significance identified as a Five Facet Mindfulness Questionnaire Observe Scale score of  $> 15.03$ . Thus, based on these effects in our pilot work testing the LA&E predictions, we anticipate that the proposed sample size for this supplemental project of  $N=90$  will be sufficient to detect medium to large effects (at the  $\alpha < .05$  level). Hypotheses 1a-1c would be supported if an interaction effect emerges (significant at the  $\alpha < .05$  level) and one or more of the within group effect sizes (of the moderator on the primary outcome) are medium or large.

*For Aim 2 of this supplemental study*, the primary mediator measures are: (1) a Numerical Rating Scale assessing characteristic pain intensity (in the past week); (2) the PROMIS Depression scale; and (3) the PROMIS Anxiety scale. Additional secondary mediators, selected per the primary mechanisms examined in the parent study (e.g., catastrophizing, mindfulness, activity level), will also be explored in the supplemental project sub-sample. The association between treatment-related changes in the primary mechanisms on changes in outcome will be tested via three PROCESS tests with 5,000 bias-corrected bootstrap resamples. The PROCESS bias-corrected bootstrap approach has been shown to consistently be the most powerful test of mediation (i.e., compared to the Sobel test, Baron and Kenny's approach) and is appropriate for small sample sizes. We will examine the significance of each path to determine if treatment condition has a differential effect on the mediator and/or outcome (although treatment-related differences in outcome are not expected), and whether early change in the mechanism is associated with later change in outcome. In the instance of a possible specific vs. shared mechanism effect, post-hoc associations will be tested via correlations to identify estimates of effect sizes for descriptive purposes.

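### The Aim 1 support rule does not say which interaction, arm or direction counts; the false-positive rate per hypothesis is 5% if the omnibus test is required and about 8-12% if any single term suffices

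*Protocol*

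**What the plan says.** The support rule is in Protocol D6s (Statistical Analyses, Aim 1). It has two parts joined by *and*: "Hypotheses 1a-1c would be supported if an interaction effect emerges", significant at .05, and "one or more of the within group effect sizes (of the moderator on the primary outcome) are medium or large".

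The same section describes the test in two ways:

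- **As one test per moderator.** "The Aim 1 supplemental hypotheses will be tested via a series of three OGRS tests". Section A2a expands the acronym: "we will use omnibus groups regions of significance (OGRS) tests to evaluate the effect sizes".
- **Term by term.** "Indicator coding will be used and these tests will be interpreted in the context of point estimates and confidence intervals". Effect sizes and Johnson-Neyman probing then follow for "any moderation main effects or interactions emerging that have confidence intervals that do not contain zero". The pilot results in D6s report a single contrast, MM vs. MBCT in a three-arm trial, as an interaction effect, with its own coefficient, p-value and interval.

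The hypotheses in A2a are more specific than the rule. Hypothesis 1a reads: "Higher baseline levels of catastrophizing will be associated with greater reductions in opioid use in response to the CT intervention compared to MM or AS". Hypotheses 1b and 1c have the same form, with AS and MM as index arms. The support rule repeats neither the arm nor the direction.

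Neither document names a reference arm, a gating step or an adjustment for several terms. The SAP covers proportions with changed dose (chi-square) and mean changes in secondary outcomes (ANOVA). It contains no moderation analysis.

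**The concern.** A three-arm model has no single interaction coefficient. It has two under indicator coding and three pairwise slope differences in all. A rule satisfied by the appearance of one interaction at .05 can therefore be met in several ways, and its error rate depends on which ways are allowed. The plan leaves that choice open until the data are in hand.

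The effect-size condition looks like a safeguard, but it applies to any arm and either sign. With 24-30 people per arm, a null correlation often reaches a medium size by chance.

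These are the primary hypotheses, and Protocol section I expects the moderation findings to inform algorithms for matching patients to treatments. A moderator with no effect could be reported as a matching variable more often than a reader would take .05 to mean. It could also be reported on the strength of a contrast that does not involve the hypothesised arm.

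**Working it through.** **Inputs.** From the protocol: three arms with equal chance of allocation (D1, D6k); 90 enrolled and 72 with complete data after 20% loss (D5), so 30 or 24 per arm; level .05 (D6s). Assumed, because the documents do not say: two-sided tests, normal errors with equal variance, and medium meaning a within-arm |r| of at least .30.

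**Formulas.** Fit outcome on arm, moderator and their product, giving slopes b for the three arms, pooled residual variance s² and N − 6 degrees of freedom (84 or 66). S is the within-arm sum of squares of the moderator.

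- Pairwise term: t = (b_j − b_k) / √[s²(1/S_j + 1/S_k)].
- Omnibus test: F = [Σ S_j(b_j − b̄)² / 2] / s², on 2 and N − 6 df, where b̄ is the S-weighted mean slope.

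**Reproducing .05.** It is recovered when the interaction means one test. In 60,000 simulated null trials the omnibus F rejects in 5.03% (30 per arm) and 5.00% (24 per arm). A single pre-named pairwise contrast rejects in 5.00% and 5.06%.

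**If any one term counts.**

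- Two terms sharing a reference arm have correlation .5 under the null; the bivariate normal gives 9.07%. The bound under independence is 1 − .95² = 9.75%.
- For three pairwise terms, the studentized range at √2·t gives 12.13% (84 df) and 12.10% (66 df). The bound under independence is 1 − .95³ = 14.3%.

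**With the effect-size condition** (simulated; 30 / 24 per arm):

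| Reading of the rule | Interaction alone | Plus a medium within-arm effect in any arm |
|---|---|---|
| Omnibus 2-df test | 5.03% / 5.00% | 5.01% / 5.00% |
| Either of two indicator terms | 9.08% / 9.13% | 8.32% / 9.03% |
| Any of three pairwise terms | 12.04% / 12.04% | 10.95% / 11.90% |
| Index arm beats either comparator, predicted direction | 4.53% / 4.66% | 4.14% / 4.60% |
| Index arm beats both, predicted direction | 0.48% / 0.48% | 0.47% / 0.48% |

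**Why the second condition protects little.** At least one null within-arm |r| reaches .30 in 28.5% / 39.3% of trials. Among trials with any significant pairwise term, the share is .1095/.1204 = 91% and .1190/.1204 = 99%. If a large effect (|r| of at least .50) were required, the any-term rates would fall to about 1-3%, but the rule accepts medium.

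**Wrong contrast, wrong direction** (interaction alone).

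- With the index arm as reference, trials where only the two non-index arms differ make up 12.04 − 9.08 = 2.96 points (30 per arm) and 12.04 − 9.13 = 2.91 points (24 per arm). In about 3% of null trials, 1a would rest on MM vs. AS alone.
- Trials where the index arm differs from a comparator only in the unpredicted direction make up 9.08 − 4.53 = 4.55 points and 9.13 − 4.66 = 4.47 points.

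**Power** (simulated; standardised slopes .5 in the index arm and 0 in the others):

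| Rule | N=90 | N=72 |
|---|---|---|
| Any of three pairwise terms, uncontrolled | 66-67% | 57-58% |
| Index arm vs. mean of the other two | about 60% | about 50% |
| Omnibus 2-df test | about 50% | about 41% |

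**The case against.** The best defence is that the plan already means one test. A2a and the Précis call the method omnibus, and D6s counts three tests for three moderators. If the 2-df test decides, alone or as a gate before the pairwise terms, the rate is 5%. The sentence about intervals excluding zero governs when effect sizes are computed and probed, not when a hypothesis is supported. The pilot text does not say whether an omnibus test came before the contrasts it reports.

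A second defence is that the hypotheses name an arm and a direction. If the rule inherits both, the interaction rate is 4.5-4.7% (either comparator) or about 0.5% (both).

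A third is that .05 is attached to the interaction, not to the rule as a whole.

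All of this stands as far as it goes. A reader might infer that the plan demonstrably runs at twice its stated error rate, or that it breaches a family-wise level across 1a-1c. The documents support neither inference: the any-term reading is not written down, and no rule-level or family-wise rate is stated anywhere.

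The defences do not remove the ambiguity. The support sentence requires no omnibus test, arm or direction. A 2-df F test has no interval that could exclude zero, so the interval wording fits single terms. The pilot, which D6s offers as the precedent for this approach, calls one pairwise term an interaction effect in the same paragraph as the rule. The SAP does not settle the matter.

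**Conclusion.** The rule is under-specified in a way that changes its error rate. Per hypothesis, the false-positive rate is 5% under the omnibus reading, about 8-9% if either of two indicator terms suffices, and about 11-12% if any of three pairwise terms does. The term-by-term reading is plausible, and arguably the more natural one given the interval and pilot wording, but it remains an inference.

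The any-term figures rest on normal errors, equal arms of 24-30 and a medium cut-off of |r| ≥ .30, which the documents do not give. Skewed MME changes could move them.

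Apart from the rate, the written rule admits support for a hypothesis from a contrast that excludes its index arm, or from an effect opposite to the prediction. That goes beyond missing detail, because the rule does not test what the hypotheses state.

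**What to change.** In the Aim 1 support sentence of D6s, define support for each hypothesis by one planned contrast from the model already specified: the index arm's moderator slope against the mean of the other two slopes (CT for 1a, AS for 1b, MM for 1c). Require significance at two-sided .05 and the direction stated in A2a. Under the null, support then occurs in at most .05/2 = 2.5% of trials per hypothesis. State the numerical cut-off for a medium effect if that condition is kept.

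Report the individual pairwise interactions with intervals as description that cannot by itself support a hypothesis. This matters because the planned contrast can be driven by one comparator only.

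Carry the rule into the SAP, which needs a new moderation section rather than a rewording. The SAP is dated July 2024 and describes its outcome comparisons in the past tense, so the addition should say whether moderation results had already been seen.

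The cost is text only, with no new data and the same fitted model. Nominal power is about 6-8 points below the uncontrolled any-of-three rule in the scenario shown. Gating on the omnibus test would also control the interaction at 5%, but it costs more power and fits the stated hypotheses less closely.

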## PRÉCIS

### **Study Title: Mechanisms of Psychosocial Treatments on Opioid Use in Chronic Pain**

#### **Objectives**

The goal of this administrative supplement is to examine the mediators and moderators of three psychosocial treatments for chronic pain, in the context of a population at risk for opioid misuse: Cognitive Therapy [CT], Mindfulness Meditation [MM], and Activation Skills [AS]. The sample will consist of 90 individuals with heterogeneous chronic pain who are at risk for opioid misuse. Participants will be randomly assigned to eight (8), 1.5 hour telehealth group sessions of (1) CT, (2) MM, or (3) AS. Mechanisms and outcomes will be assessed twice daily during 2-week baseline, 4-week treatment period, and 4-week post-treatment epoch via cue-elicited ecological momentary assessment (EMA) and via weekly telephone interviews during this time period; activity level will be monitored during these time epochs via daily monitoring with ActiGraph technology. Follow-up macro-level assessments will be conducted at 3- and 6-months post-treatment. The study will address two aims.

**Aim 1** is to test the Limit Activate and Enhance (LA&E) model to investigate theory driven moderators of response to CT, MM and AS in a sample of individuals with chronic pain at risk for opioid misuse. To accomplish Aim 1, we will use omnibus groups regions of significance (OGRS) tests to evaluate the effect sizes associated with the extent to which baseline pain catastrophizing, mindfulness and activity level are respectively associated with reductions in opioid use following CT, MM and AS. Specifically, three OGRS models will test the LA&E predictions that (1) higher baseline levels of catastrophizing will be associated with greater reductions in opioid use in response to the CT intervention compared to MM or AS (Hypothesis 1a), (2) lower baseline levels of activity will be associated with greater reductions in opioid use in response to AS compared to CT or MM (Hypothesis 1b), and (3) higher baseline levels of non-judgment will be associated with greater reductions in opioid use in response to MM compared to CT or AS (Hypothesis 1c). We will test these baseline characteristics as moderators of response at post-treatment (primary analyses) and at 1-, 3- and 6-month follow-up (secondary analyses).

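### The D6s support rule for Hypotheses 1a-1c leaves out the arm and direction that define each hypothesis, so read literally a reversed effect counts as support exactly as often as the predicted one

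*Protocol*

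**What the plan says.** Protocol A2a gives each Aim 1 hypothesis a named arm and a direction:

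- 1a names CT: "Higher baseline levels of catastrophizing will be associated with greater reductions in opioid use in response to the CT intervention compared to MM or AS".
- 1b names AS: "Lower baseline levels of activity will be associated with greater reductions in opioid use in response to AS compared to CT or MM".
- 1c names MM: "Higher baseline levels of non-judgment will be associated with greater reductions in opioid use in response to MM compared to CT or AS".

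The Précis (Objectives) repeats them and says that "three OGRS models will test the LA&E predictions that" these patterns hold, so the intent is directional.

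In D6s the outcome is defined: "The primary outcome will be baseline to post-treatment change in opioid use, as assessed in MMEs". Each moderator gets one omnibus groups regions of significance (OGRS) test, with indicator coding and no reference arm named. D6s adds that "these tests will be interpreted in the context of point estimates and confidence intervals". Effects whose interval excludes zero are probed by the Johnson-Neyman method.

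The decision sentence in D6s reads "Hypotheses 1a-1c would be supported if an interaction effect emerges" at the .05 level and "one or more of the within group effect sizes (of the moderator on the primary outcome) are medium or large". It gives no arm, sign, contrast or reference group, and no number for medium.

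The SAP, dated July 2024 and written in the past tense, covers dose-change categories, chi-square comparisons and an ANOVA of secondary outcomes. It contains no moderation analysis and no support rule.

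**The concern.** For Aim 1, the arm and the direction are the content of each hypothesis. A result in which low catastrophizers do better in CT, or in which catastrophizing matters only in MM, is not evidence for 1a. The rule as written accepts both, because any significant interaction and any sufficiently large within-arm effect will do.

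What is at stake is the pre-stated verdict on a primary aim. Section I of the Protocol says that the moderation findings are meant to inform patient-treatment matching, and for matching a verdict that cannot tell a pattern from its reverse is of little use. The defect goes no further than that verdict. The rule allocates no participant, and the slopes and intervals would be reported whatever it says.

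**Working it through.** **No stated figure to reproduce.** D6s says N = 90 is sufficient for medium to large effects but gives no power value and no numeric effect size. The usable inputs are:

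- 90 enrolled (D5) and three arms with equal chance of assignment (D6k): 90 / 3 = 30 per arm, taking equal arms.
- 20% loss (D5): 90 × 0.80 = 72, or 24 per arm.
- Alpha .05 (D6s).
- Assumptions that are not in the documents: medium means |r| ≥ .30, normal data, and a true effect in one arm only (slopes of 0 in the others).

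**Model.** For arm g, change = a_g + b_g × moderator + error. The candidate tests are:

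- Omnibus: F = [(SSE with a common slope − SSE with separate slopes) / 2] / [SSE with separate slopes / (N − 6)].
- Pairwise or indicator-coded: t = (b_g − b_h) / SE(b_g − b_h).
- Effect-size clause: |r_g| ≥ .30 in at least one arm.

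**Reversed effect, by algebra.** Replace the moderator by its negative. Every b_g and r_g changes sign, while F, |t| and |r_g| do not. A reversed effect of equal size therefore passes with exactly the same probability under every reading of the test. This needs no simulation and no cut-off.

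**Wrong-arm effect, by algebra.** With equal arms, relabelling the arms leaves F, the set of all pairwise |t| values and the largest |r_g| unchanged. The pass rate is therefore equal under the omnibus and any-pairwise readings. It is not equal if the interaction is one set of coefficients against a single fixed reference arm, because that arm enters both contrasts.

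**Size, by simulation** (40,000 to 100,000 trials per setting; at 40,000 the standard error near 50% is √(.25/40,000) = 0.25 points). Percentage of trials in which the literal rule declares support:

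| Reading | Per arm | r | Predicted | Reversed | Wrong arm |
|---|---|---|---|---|---|
| Omnibus | 30 | .5 | 50.4 | 50.1 | 50.2 |
| Omnibus | 30 | .3 | 19.4 | 19.8 | 19.5 |
| Omnibus | 24 | .5 | 41 | 41 | 40 |
| Any pairwise | 30 | .5 | 66 | 67 | 66 |
| Indicator, named arm as reference | 30 | .5 | 66 | 66 | 51 |
| Indicator, a wrong arm as reference (effect in that arm) | 30 | .5 | 51 | 51 | 66 |

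The small differences between predicted and reversed are simulation noise. Opposing slopes give the same picture: with −.25 in the named arm and +.25 in both others, a full reversal, the omnibus reading declares support in 49% of trials at 30 per arm.

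**Illustration from the Protocol.** The first pilot effect in D6s is a significant interaction in which people with low catastrophizing improved more in one arm (r = −.36). If medium is .30, it satisfies both clauses, although its direction is opposite to 1a and its arm is not CT. That pilot used pain intensity as the outcome and an arm absent from this trial, and the Protocol does not present it as support for 1a. It shows only what the wording admits.

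**The case against.** The strongest reply is that the rule says when Hypotheses 1a-1c are supported, and those hypotheses already carry arm and direction in A2a. A careful analyst would import them, and point estimates, intervals and Johnson-Neyman regions would expose a reversal. This stands as a limit on the harm. It does not repair the rule, because a pre-stated criterion should not depend on what its reader adds. The Aim 2 criterion in D6s does write out the pattern that separates 2a from 2b, although it too states no sign for the mechanism-outcome effect.

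A second reply is that D6s does not code MME change as positive or negative, but A2a says in words that the prediction is a greater reduction. That is correct. Coding is not the problem, and the fix can be worded in terms of reduction.

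Two stronger readings are tempting and are not supported:

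- A reader might infer that a wrong-arm effect always passes as often as the predicted one. D6s specifies indicator coding, and its pilot text uses the term interaction effect for a single pairwise coefficient. Under a fixed reference arm the two rates can differ in either direction.
- A reader might infer that the investigators would knowingly call a reversed effect support. Nothing in the documents says so, and the Précis points the other way.

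**Conclusion.** The point holds and should be fixed. The D6s rule omits the arm and direction that A2a gives each hypothesis, and neither the rest of D6s nor the SAP supplies them. For a reversed effect of equal size, the equality is exact under any reading. For a wrong-arm effect the rate is equal under the omnibus or any-pairwise reading with equal arms. Otherwise it is lower or higher, depending on a reference arm the Protocol does not name, and it is about 51% even in the lower case at r = .5 and 30 per arm.

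The percentages rest on the assumed cut-off of .30, normal data, equal arms and a one-arm effect; the omission does not. The consequence is an unreliable label on a primary aim. The estimates themselves are not biased.

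**What to change.** Keep the plan's interaction test and effect-size clause. Add to D6s, and carry into the SAP, that a hypothesis is supported only if, in addition, the named arm's slope has the predicted sign in terms of MME reduction and exceeds both other arms' slopes in that direction:

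- 1a: CT slope positive on catastrophizing and the highest of the three.
- 1b: AS slope negative on activity and the lowest.
- 1c: MM slope positive on non-judgment and the highest.

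Report any other significant interaction as unpredicted, and a reversed one as evidence against the hypothesis.

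Effect on declared support at 30 per arm (current → with the addition):

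| Truth | Omnibus | Any pairwise |
|---|---|---|
| Predicted, r = .5 | 50.4% → 49.7% | 66.3% → 65.3% |
| Predicted, r = .3 | 19.4% → 18.1% | 32.2% → 29.6% |
| Reversed, r = .5 | 50% → about 0% | 67% → about 0% |
| No effect | about 5% → 1.6% | about 11% → under 4% |

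One limit remains. A slope of −.5 in one other arm alone still passes in about 23% (omnibus) or 29% (any pairwise) of trials, when the named arm's slope happens to come out positive and highest.

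Two matters are separate choices for the authors and not part of this fix. The first is whether the interaction means the omnibus 2-df test or a pairwise coefficient; requiring the omnibus test where pairwise now counts would cut true support from 66% to 50% at r = .5. The second is whether the effect-size clause applies to the named arm. Under the omnibus test that would reduce the −.5 wrong-arm case to about 5%, but with slopes of +.25, −.25 and −.25 it would cut true support from 49% to 33%.

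The change is wording only and needs no new data. Because the SAP is dated July 2024 and written in the past tense, date and disclose the change, and label it post hoc if moderation results have been seen.

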**Aim 2: Examine the mediators underlying the expected change in opioid use during treatment.**

To accomplish Aim 2, we will use PROCESS bootstrap mediation models to evaluate the extent to which early treatment changes in the primary mechanisms (pain intensity and emotional distress, i.e., depression and anxiety) will predict subsequent late-treatment changes in opioid use (primary outcome), and the extent to which these associations are shared across the three treatments, or if some are unique to one or a subset of treatments.

**Hypothesis 2a:** If changes in pain intensity and emotional distress are mechanisms shared by CT, MM, and AS, then changes in opioid use in all three treatments will be predicted to approximately the same extent by changes in the primary mechanisms.

**Hypothesis 2b:** If changes in the primary mechanisms are *specific* to one (or a subset) of the three treatments, then Treatment Group X Assessment Period interactions will reveal that late-treatment changes in opioid use will be substantially and uniquely predicted by early-treatment changes in the primary mechanism(s) in one (or a subset) of the three conditions only.

We also predict that change in the mechanism variables will precede and predict change in outcome, but not vice versa.

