We applied this approach to the three active treatments in pilot data obtained in our RCT comparing CT, Hypnosis and Hypnotic-CT (within the subsample of participants who reported musculoskeletal pain who were prescribed opioids,  $N=18$ ) to examine the relative statistical power achieved in that sample to detect medium to large effects for the analyses planned for this supplemental project. In two PROCESS models testing if early change in pain intensity or depression were specific vs. shared mechanisms in accounting for late treatment change in opioid use, results showed: (1) a non-significant effect of condition on outcome (path *c*) as well as on both mechanisms (path *a*); and (2) a significant effect of both mechanisms on the outcome (path *b*;  $ps < .01$ ). Post-hoc correlations were then conducted for descriptive purposes. We found that early change in both pain intensity and depression were significantly associated with later change in opioid use across groups ( $rs = .58$  and  $.68$ , respectively); on the other hand, early change in outcome was not significantly associated with later change in mechanism. Taken together, these results (1) provide support for early change in pain intensity and depression as underlying later reductions in opioid use, and (2) are consistent with a shared mechanisms account for the role of early change in pain intensity and depression as mechanisms driving decreased opioid use across the treatments studied in this pilot data. The proposed sample size and procedures of the supplemental project will afford the capacity to test these associations more definitively.

Overall, our pilot data indicate that if changes in outcome and mechanisms in the supplemental project are medium to large in nature, then the sample size of  $N=90$  will be adequate to test the mediation hypotheses 2a and 2b. Support for Hypothesis 2a and the shared mechanisms conceptualization would be found in the instance of a non-significant effect

of condition on the mechanism variable, but significant ( $\alpha \leq .05$ ) effect of the mechanism on outcome collapsed across groups. Support for Hypothesis 2b on the other hand would be found in the instance of a significant effect of condition on the mechanism, with change in the mechanism differentially associated with change in outcome across treatment conditions.

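### The decision rule for Hypothesis 2a (shared mechanism) does not compare mechanism-to-opioid slopes between arms, and the protocol gives shared two different meanings

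*Protocol*

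**What the plan says.** **Hypotheses (Précis, Aim 2; section A2a).** Aim 2 asks about "the extent to which these associations are shared across the three treatments, or if some are unique to one or a subset of treatments". Under 2a, "changes in opioid use in all three treatments will be predicted to approximately the same extent by changes in the primary mechanisms". If a mechanism is specific, "then Treatment Group X Assessment Period interactions will reveal that late-treatment changes in opioid use will be substantially and uniquely predicted by early-treatment changes" in one arm or a subset of arms (2b).

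**Decision rules (section D6s).** For 2a, the first requirement reads "Support for Hypothesis 2a and the shared mechanisms conceptualization would be found in the instance of a non-significant effect", meaning the effect that treatment arm has on the mediator (path a). The second is a significant (α ≤ .05) "effect of the mechanism on outcome collapsed across groups". For 2b, the first requirement reads "Support for Hypothesis 2b on the other hand would be found in the instance of a significant effect of condition on the mechanism". A second requirement, the only slope comparison in these rules, is then added: "with change in the mechanism differentially associated with change in outcome across treatment conditions".

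**Models (section D6s).** The PROCESS models examine condition on mechanism (path a), condition on outcome, and mechanism on outcome (path b). No condition-by-mechanism term is named, and the follow-up correlations are descriptive. The N=18 pilot, with a non-significant path a and a significant path b, is read in the same way: its results "are consistent with a shared mechanisms account for the role of early change in pain intensity and depression as mechanisms".

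**Post-treatment hypotheses (section A2b).** The shared model, labelled there as Hypothesis 2a, is carried into the post-treatment period. Exploratory Hypothesis 3a states it as small, non-significant effects of condition on early change in the mechanism.

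**SAP.** It covers categories of MME change and ANOVAs of secondary outcomes. It contains no mediation analysis.

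**The concern.** Section A2a words 2a as a statement about slopes: a given change in the mechanism goes with about the same change in opioid use in each arm. The D6s rule for 2a tests something else. Path a asks whether the arms moved the mechanism by different amounts. The pooled slope can be significant when only one or two arms carry the association.

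The slope comparison in D6s belongs to the 2b rule and is joined there to a significant path a. When the arms move the mechanism equally, path a is significant only about 5% of the time. A slope difference then seldom leads to a specific verdict, and nothing stops a shared verdict.

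Shared versus specific is the contrast between 2a and 2b. The trial could report a mechanism as common to CT, MM and AS against its own slope data. Whether early mechanism change predicts later opioid change, and the temporal order of change, are not affected.

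**Working it through.** **1. The plan's own figures.** Section D6s calls N=90 adequate for 2a and 2b if effects are medium to large, but gives no power value or slope difference to reproduce. The attrition figure in D2 and D5 does reproduce: 90 × (1 − 0.20) = 72. Equal arms give 72/3 = 24 or 90/3 = 30 per arm. Results below are shown as 24/30 per arm.

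**2. Slopes must be assumed.** The only related figures are pilot correlations pooled over arms. For r = .58, N = 18: Fisher z = 0.662, standard error 1/√15 = 0.258, 95% limits 0.156 and 1.169, which back-transform to r = .16 to .82. Both .3 and .6 lie inside.

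**3. The rule as tests.** Data are normal and standardised, with no true arm difference in mechanism change. Alpha is .05, taken as two-sided because D6s does not say.
- Path a: F = (SSB/2)/(SSW/(N−3)).
- Common slope on arm-centred values: b = Σmy/Σm², t = b/√[(RSS₀/(N−4))/Σm²].
- Slope difference: F = [(RSS₀−RSS₁)/2]/[RSS₁/(N−6)], where RSS₁ allows a slope per arm.
- Shared: path a p ≥ .05, common slope p < .05 and positive. Leaving arm out of the slope model changes rates by at most about 3 points.
- 2b: path a p < .05 and slope-difference p < .05.

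**4. Results (about 20,000 simulated trials per case).**

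| Assumed slopes | Shared declared | Shared despite significant interaction | 2b declared |
|---|---|---|---|
| .6/.6/0 | 88%/92% | 53%/66% | 2.8%/3.7% |
| .5/.5/0 | 77%/84% | 32%/44% | 1.9%/2.6% |
| .3/.3/0 | 36%/44% | 5%/9% | 0.8%/1.1% |

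Repeat runs agree to within about 2 points. With association in one arm only, shared is declared in 37%/45% (.6/0/0) and 12%/15% (.3/0/0), and against a significant interaction in 20%/29% and 1.7%/2.5%.

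**5. Hand check for .5/.5/0.** With equal path a, P(shared) ≈ 0.95 × P(common slope significant). At 30 per arm, 0.95 × 0.886 = 0.842 (simulated 0.844). At 24 per arm, 0.95 × 0.817 = 0.776 (simulated 0.780). For 2b, 0.05 × 0.531 = 0.027 (simulated 0.025) and 0.05 × 0.424 = 0.021 (simulated 0.021).

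**6. Sensitivity for .6/.6/0.** Shared falls to 56%/50% if the two active arms also move the mechanism 0.5 SD more, and to 18%/10% at 0.8 SD. With half of MME changes set to zero at random (an assumed share), it is 63%/72%, and 22%/30% despite a significant interaction.

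**The case against.** The strongest reply is that path a belongs to what the protocol means by shared. Section A2b labels the shared model Hypothesis 2a and states it through similar condition effects on the mechanism, as D6s does. The premise of 2b in A2a, that changes in a mechanism are specific to some treatments, can also be read as differential mechanism change. A group-by-period interaction literally compares change over time between arms. This stands. It makes the defect an inconsistency between the Précis and A2a on one side and A2b and D6s on the other, and the documents do not say which governs.

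Three stronger readings are therefore not supported.
- A reader might infer that slopes are compared nowhere. The D6s rule for 2b does ask for differential association; that comparison simply does not govern 2a.
- A reader might infer that A2a settles the meaning and that similar mechanism change belongs only to Exploratory 3a. Section A2b ties the two together.
- A reader might count a true 2a withheld as a second harm. With equal slopes of .6 and one arm moving the mechanism 0.5 SD more, shared is withheld in 40%/49% of trials. That is an error only if 2a is purely about slopes, so it is not counted.

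It is also fair to object that the slopes are assumed, that an arm with exactly zero association has no support in the documents, and that declaring shared against the trial's own interaction is uncommon at small slopes. The mismatch between hypothesis and rule needs no assumed slope; its frequency does.

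**Conclusion.** The point holds and should be fixed. As written, the D6s rule can label a mechanism shared without comparing slopes, although the Précis and A2a define 2a by comparable prediction in each arm. The SAP does not resolve this.

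The size depends on the scenario. At 24 to 30 per arm with equal mechanism change, the rule declares shared despite unequal slopes in most trials when the slopes are .5/.5/0 or .6/.6/0, and in roughly two in five at .3/.3/0. Contradiction by a significant interaction in the same data ranges from about 5%/9% to 53%/66% across those three cases. These rates rest on assumed slopes, normal data and equal arms. They fall if the active arms also move the mechanism more or if many MME changes are zero.

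**What to change.** For each primary mediator (pain intensity, depression, anxiety):

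1. Keep the D6s requirement of a significant mechanism-to-outcome slope. Without it, a mechanism that predicts nothing could pass: with slopes 0/0/0 the interaction is non-significant in about 95% of trials, whereas the present rule, with the slope also positive, declares shared in about 2.5% (0.95 × 0.025 = 2.4%).
2. Add a model of late-treatment MME change on early mechanism change, arm and arm × mechanism change, with HC3 or bootstrap inference. If half the changes are zero, the ordinary interaction test rejects truly equal slopes of .6 in 11.0%/11.5% of trials, against 6.8%/6.7% with HC3.
3. Report the three arm-specific slopes and their pairwise differences with 95% confidence intervals. Let the joint 2-df test decide and the intervals describe: under equal slopes, at least one of three bootstrap intervals excludes zero in 15% to 17% of trials.
4. Do not declare 2a when the joint interaction is significant. When it is not, say that slopes were not shown to differ and give the intervals. Do not claim sameness unless a similarity margin was stated beforehand.
5. Report path a separately. State whether shared means equal slopes, equal mechanism change, or both, and use that meaning in the Précis, A2a, A2b and both D6s rules.
6. Note that three mediators are tested: 1 − 0.95³ = 14% familywise if the tests were independent. The SAP is dated July 2024 and written in the past tense, so label the rule post hoc if it was set after data were seen.

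**Cost.** One model per mediator on data already collected, and an Aim 2 section in the SAP. The gain is partial: for .5/.5/0, blocking 2a on a significant ordinary interaction lowers shared declarations from 84.4% to 40.3% at 30 per arm (84.4 − 44.1) and from 78.0% to 46.0% at 24 per arm (78.0 − 32.0). HC3 interaction power is 51%/63% for .6/.6/0 and 15%/19% for .3/.3/0, so 2a will often be inconclusive.
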